2.3.3 ASSESSMENT OF POTENTIAL RISKS AND BENEFITS

This study is of minimal risk to participants. It is possible that some youth may find some of the survey questions too sensitive or uncomfortable. Participation is voluntary; participants are reminded that they can stop participating at any point. Youth are provided with relevant resources at the end of each survey. The youth surveys are anonymous. That is, youth produce a self-generated personal code based on 8 nonidentifiable questions (e.g., first letter of mother's first name) to ensure responses will remain as anonymous as possible and can be matched across data collection points. No names or linking information will be connected to the surveys.

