4 STUDY DESIGN

4.1 OVERALL DESIGN

This study design involves a two-arm cluster-randomized-controlled pilot feasibility trial conducted with adolescents ages 13-17 recruited from youth-serving community agencies in Pittsburgh, PA and their self-identified adult supports. Sites in four neighborhoods were randomly allocated to the intervention or control arm. Sites were selected based on participation as control sites in a previous cluster-randomized trial (NCT02427061). All neighborhoods in the study met criteria as socially or economically disadvantaged. Randomization was performed at the neighborhood level (i.e., cluster) to reduce risk for contamination. The randomization included 4 clusters that were assigned to experimental or control conditions. The study statistician performed this randomization such each site/neighborhood had a 50/50 chance of being assigned to intervention or control. Participants (anticipated n=50 youth, 25 adults) complete surveys prior to program implementation (baseline) and immediately following the program (end of program, EOP). Baseline surveys are completed in-person using tablets to complete the survey online. EOP surveys are also completed in-person on a tablet or remotely using survey links that are texted or emailed to participants using contact information provided with recruitment. We will also conduct semi-structured interviews with a subsample of adolescent-adult dyads in the intervention arm (n=5-8) to further assess acceptability and guide refinements for a larger effectiveness trial. Retention is facilitated by collecting detailed contact information and offering incentives for survey completion.

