6.2 FIDELITY

6.2.1 INTERVENTIONIST TRAINING AND TRACKING

Facilitators at the community-partner sites will be trained on the intervention curriculum by study personnel prior to launch of the study. Pilot testing before the start of the study will allow study staff to finalize the curriculum and training necessary to begin the intervention. The facilitators that are chosen for this study have experience being facilitators in similar research studies. Research personnel will attend every session and complete fidelity feedback forms on the structure and completion of the session. Surveys will also be given to the facilitators to review their participation and program leading for the intervention. Sessions will be tracked in an online database and on the research database with session updates, upload of fidelity forms, and study tracking. Survey tracking from REDCap will be completed through the database and on REDCap.

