8 STUDY ASSESSMENTS AND PROCEDURES

8.1 ENDPOINT AND OTHER NON-SAFETY ASSESSMENTS

Assent and Consent

Youth ages 13-17 receive a description about the research study and parental letter about the study from the community sites. The parent letter includes an option for parents/caregiver to decline their child's participation. We received a waiver of parental permission and waiver of signed consent from the University of Pittsburgh Human Subjects Research Protection Office. Research assistants review the verbal consent form with youth at the beginning of the first session and answer any questions pertaining to confidentiality, the program flow, and survey time points. The consent form covers all research surveys over the course of the program. An additional consent is used for the optional interview portion at the end of the project.

Data Collection

There are several points of data collection throughout the study including baseline surveys, feedback forms, End of Program (EOP) survey, and interview. The surveys are all anonymous, linked by a personal secret code that youth create by answering a series of questions that only they know the answer to at the beginning of each survey. This method of using a personal study code was selected to ensure anonymity and increase the likelihood of honest responses. In addition to survey data, other sources of data for this study (primarily for process evaluation and assessing intervention fidelity) include: 1) feedback forms completed by youth after the end of each session; 2) fidelity forms completed by research assistants at each session; 3) interviews with site leads and facilitators; 4) interviews with youth.

Main Study Phase

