Baseline survey: Youth are asked to complete the baseline survey the first time they attend a session (can enter study at Sessions 1 – 3; if participant is interested in joining after session 3, they are asked to return for the next round). All sites conduct web-based surveys (back up paper surveys are used as needed) on tablets using REDCap, an online data management and survey system. Responses to the anonymous web-based secure survey are entered by the youth participants themselves on an electronic tablet; no data are stored on the computers themselves. Only research staff who have been added to the project can access this online database. Data are downloaded and stored on a password-protected share drive that can only be accessed by users with the appropriate permissions. No names are connected to the survey data as each participant creates their own secret code as described above.

End of program survey: At the end of the program, youth are asked to complete an end of program survey that asks about which sessions they attended, their impressions of the program, and reassesses measures collected on the baseline survey. Surveys are self- administered on electronic tablets provided by the research staff (back up paper surveys will be used if tablets are not available or fail). All participants, regardless of the amount of curricular content completed, are eligible to take this survey; participants are asked to complete the end of program survey later if they miss the last session.

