Emailed/text survey option: Participants who cannot attend the study site or other community site (e.g., due to lack of transportation, neighborhood barriers) for EOP survey administration will be offered the option to take the survey via email or a texted link on an internet-capable device (e.g., computer, smartphone). The RA will confirm via phone that the participant is OK to take the survey. The link will be specific to the email address that the young person provides and will only allow the survey to be taken once. Using REDCap's anonymous survey feature, we can create an individualized link to be sent to each participant's email or phone, and confirm if their survey was completed, but we cannot determine which survey data corresponds to that participant (i.e., remains anonymous). Phone call option: participants can also opt to complete the survey during a phone call with a research assistant, who reads aloud the questions and the participant responds; the research assistant enters the answers directly into the online survey tool.

Alternate contact information: We will also use the alternate contact information provided by youth upon study enrollment to reach them for follow-up surveys. This may include, but is not limited to, phone numbers or email addresses for parents, caregivers, other family members, and close friends. We then ask these contacts to facilitate us reaching the participant. Community site partners from the program are also contacted to ask for retention assistance.

Interviews: At or after the EOP survey, some youth will be invited to participate in a confidential interview about their experiences receiving the control or intervention, their feedback about the relevance of the program, and additional input about the impact of the program on themselves and their peers. The interviews will be digitally recorded, transcribed, and the audio files destroyed once the transcription has been checked for accuracy and all identifying information removed.

Data Management

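### The read-aloud phone option for the end-of-program survey removes anonymity at one time point only, and the plan neither records nor analyses survey mode

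*Combined protocol and SAP*

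**What the plan says.** **Baseline.** Under the baseline survey paragraph of Section 8.1, "Responses to the anonymous web-based secure survey are entered by the youth participants themselves on an electronic tablet", with paper as back-up. No phone mode is described for baseline. The self-entry statement recurs under Data Management in 8.1 and, in similar terms, under Data Security in 8.2.

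**End of program.** The default in 8.1 is again self-completion: "Surveys are self- administered on electronic tablets provided by the research staff". Participants who cannot attend are offered an emailed or texted link. For that link, 8.1 explains that staff can see whether a survey was completed but cannot tell which data belong to whom. It then adds a third route: "participants can also opt to complete the survey during a phone call with a research assistant, who reads aloud the questions", and "the research assistant enters the answers directly into the online survey tool". Section 4.1 gives only the first two routes: "EOP surveys are also completed in-person on a tablet or remotely using survey links that are texted or emailed to participants".

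**Anonymity.** The Data Collection part of 8.1 describes every survey as anonymous and linked by a secret code built from questions at the start of each survey. The reason given is: "This method of using a personal study code was selected to ensure anonymity and increase the likelihood of honest responses". Section 2.3.3 adds: "No names or linking information will be connected to the surveys".

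**Content and analysis.** The end-of-program survey repeats baseline measures. Section 9.1 lists past-30-day violence perpetration and victimization, each scored 0-9, at both time points, and overall satisfaction, scored 1-5, at end of program only. Sections 9.3 and 9.4.2 estimate outcomes within each arm. Section 9.4.9 adds a mixed-model analysis of pre-post differences, and 9.4.1 states the comparison between arms. Section 9 nowhere mentions survey mode.

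**Staff.** Research staff are not blinded (6.3). On their presence at sessions, 6.2.1 says: "Research personnel will attend every session and complete fidelity feedback forms on the structure and completion of the session".

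**The concern.** The safeguard that the protocol relies on for honest answers is in place at baseline and absent at end of program for anyone who takes the read-aloud call. A young person who reported violence privately on a tablet before the program may report less of it aloud to a staff member afterwards. The measured change then mixes any real change with a change in how the question was asked. A similar pull could act on satisfaction: someone rating the program aloud to a member of the study team may rate it higher.

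The analysis plan makes this harder to dismiss. The primary analysis, and part of the exploratory analysis, estimates each arm on its own, so equal phone use in the two arms does not cancel a shift within an arm. If mode is not recorded, nobody can check afterwards whether it mattered. Section 2.1 also says that the pilot is meant to test this way of collecting data for a larger trial, so the share who need a call is itself a useful feasibility result.

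**Working it through.** **1. The plan's own figure.** Section 9.2 states a within-arm 95% margin of error of at most 0.20 with 25 youth per arm. For a proportion of 0.5 and no clustering, 1.96 x sqrt(0.5 x 0.5 / 25) = 1.96 x 0.10 = 0.196, which agrees. The point here does not depend on this figure, but the arm size sets the scale: one participant is 1/25 = 4% of an arm, so a 20% phone share is five young people.

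**2. The modes side by side.**

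| | Baseline (tablet) | End of program, tablet | End of program, link | End of program, call |
|---|---|---|---|---|
| Who enters the answers | Youth | Youth | Participant | Research assistant |
| Do staff know whose answers they are? | No, as described | No, as described | No, stated in 8.1 | Yes, the caller does |
| Listed in 4.1 | Yes | Yes | Yes | No |

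The last column fits neither the unqualified anonymity statement nor the self-entry statements. Section 8.1 places the code questions at the start of each survey and does not exempt the call. If they are read aloud too, the caller hears the code that links this survey to the participant's baseline survey and, under 6.1.2, to the session feedback forms.

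**3. Which outcomes can be affected, and how.**
- Violence perpetration and victimization: measured at both time points, so a shift at the second enters the change. Both are exploratory.
- Overall satisfaction: measured only at end of program. Only its level can shift; it has no pre-post change.
- Attendance: recorded at sessions (9.1), so not affected.

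**4. Size within an arm.** Let f be the share of an arm surveyed by read-aloud call and d the mean amount by which those participants under-report. The arm's mean change is then shifted by -f x d. Neither f nor d is in the documents, so the values below are assumptions.

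| f | d = 0.25 | d = 0.5 | d = 1.0 |
|---|---|---|---|
| 10% | 0.025 | 0.05 | 0.10 |
| 20% | 0.05 | 0.10 | 0.20 |
| 40% | 0.10 | 0.20 | 0.40 |

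The entries are points of apparent reduction on the 0-9 score with no true change. For satisfaction the same product f x d gives the rise in the end-of-program mean on the 1-5 scale, with d read as over-rating.

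**5. Size between arms.** With the same d in both arms, the shift in the SCC-minus-control difference is -(f_SCC - f_control) x d. Taking d = 0.5:
- 20% against 20%: 0.
- 30% in SCC against 10% in control: -(0.30 - 0.10) x 0.5 = -0.10, in favor of SCC.
- 10% in SCC against 30% in control: +0.10, against SCC.

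The sign depends on which arm uses the phone more, and the documents give no basis for predicting that.

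**6. Who would use the call.** In 8.1, those who miss the last session complete the survey later, and the link is offered to those who cannot get to a site. Phone users are therefore likely, though not certain, to be less engaged. A comparison with and without them reflects mode and engagement together.

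**The case against.** The strongest reply is that the call is one opt-in route behind two self-completed ones, so few participants may use it. In a pilot with 25 youth per arm, a spoken answer may also be better than none. Staff are not wholly absent at baseline either: 6.1.1 has them available to guide participants through the survey. All of this stands. It limits the size of the problem and argues against simply removing the option.

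Several stronger readings are tempting, and the documents do not support them.

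- *Satisfaction switches mode between baseline and end of program.* It cannot, because it is asked only at the end.
- *The call biases the trial toward SCC.* The option is open to both arms. A shift would flatter Job Skills as well, and the contrast moves only if phone use or its effect differs by arm, in either direction.
- *Participants will be rating the program to the person who ran it.* The documents do not say which assistant calls. Section 6.1.1 has research staff delivering SCC, while 6.2.1 describes facilitators at the partner sites with research personnel attending. It is possible, but not established.
- *A promise of anonymity to minors is broken.* Sections 2.3.3 and 6.1.1 qualify the code as keeping answers as anonymous as possible, the call is the participant's choice, and the consent text is not available for review. The statement in 2.3.3 about names can remain true of the stored record. What does not hold for these participants is the unqualified statement in 8.1 that all surveys are anonymous.

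The direction of the violence shift is also an inference from the protocol's reasoning on honesty, not a finding in the documents. For satisfaction even that reasoning is indirect.

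**Conclusion.** The point holds in a limited form. Some participants may give end-of-program answers aloud to a research assistant after anonymous self-entry at baseline. This conflicts with the anonymity and self-entry statements in 8.1 and 8.2, and the mode is missing from 4.1. It could make violence appear to fall within an arm and could raise the level of satisfaction. The first concerns exploratory outcomes; the second concerns one of the two primary outcomes.

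The share affected and the size are unknown. Under the assumed ranges above (10% to 40% by phone, a shift of 0.25 to 1.0 points), the within-arm shift runs from 0.025 to 0.40 points. It is zero if nobody takes the call or if spoken answers match private ones. The between-arm direction is undetermined. This is an inexpensive improvement to measurement and reporting, not a threat to the trial as a whole.

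**What to change.** 1. In 8.1, make the first choice on any call a texted or emailed link that the participant completes, including the code questions, while the research assistant stays on the line to help.
2. Keep read-aloud for those who cannot use a link, with a caller who did not work at that site where possible. Ask the full survey, so that no measures are dropped and the link to baseline is kept.
3. Record the mode of every end-of-program survey (tablet, paper, link, read-aloud call).
4. In Section 9, report the phone share by arm and site, and repeat the satisfaction and violence estimates without read-aloud surveys. State alongside that this analysis also removes participants who are likely to be less engaged, so a difference cannot be put down to mode alone.
5. Reconcile 4.1, the Data Collection and Data Management parts of 8.1, and 8.2 with the phone option, both on permitted modes and on what anonymity means for someone who takes the call.

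The cost is one REDCap field, one sensitivity table, some protocol wording and slightly more effort per call.

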8.2 SAFETY ASSESSMENTS

Data Security: Responses to the anonymous web-based secure survey are entered by the youth participants themselves through a computer-based system; the data are automatically entered into a password protected database accessible only to the investigative team. No names are connected to the survey data as each participant creates their own secret code as described above. Contact forms will be stored in a secure file drawer inside the locked office of the PI's research lab whenever not in use. Contact forms will be stored separately from any survey data collected in this study (the survey data are collected via computer and immediately housed in a password-protected secure database). The names of participants will be kept in an encrypted file on a password protected secure on-line server (available to the research team through the University of Pittsburgh), and accessed only when needed to arrange the follow up data collection with each community site. Please note that there are three layers of protection for the contact information: password protection to enter the University of Pittsburgh system, a username that has been granted access to the secure drive, and another password to decode the encrypted file. This information will be accessed only when needed to arrange follow-up contact with participants and scheduling data collection.

Internal Data and Safety Monitoring Plan: Given the sensitivity of the questions being asked regarding violence perpetration, we are taking extra precautionary measures with an internal data safety and monitoring plan in place. The senior research coordinator is responsible for daily monitoring of data and safety. They will work with research assistants to ensure that all data are collected and stored securely. The research team consisting of the PI ([name]), senior research coordinator, research assistants, data analysts, and other research staff as appropriate, will meet weekly to review study progress and status of data collection and safety of participants. Each neighborhood/site has a designated point RA, who along with the research coordinator, is connected to the community site leads and can identify concerns about data collection or participant safety.

Extra precautionary measures were taken to protect the data, including the use of a personally created ID code to maintain anonymity of the survey data and an internal data safety and monitoring plan, which included the following:

- a) Systematically review assessment materials to ensure that assessment is conducted appropriately and that participants disclosing abuse or violence during the course of taking the survey receive appropriate connection to violence-related services and that mandated reports are made by site personnel when appropriate.

- b) Systematically review notes from research assistants to ensure that participants experiencing distress are being connected directly with the site directors and youth workers, receiving educational materials, and being referred appropriately; this includes ensuring that all research assistants document asking each participant about emotional distress after completion of the survey.
- c) Monitor staff performance with regard to protection of privacy, confidentiality, maintenance of secure databases, and study procedures designed to reduce the risk of distress and potential breaches of confidentiality.
- d) Ensure that the PI ([name]), or a designated qualified individual, will be available in case research staff needs to confer regarding participants' behaviors or comments made during a survey or other research activities.
- e) Ensure that the PI ([name]), or a designated qualified individual, will be available in case educators needs to confer regarding participants' or youth workers' behaviors or comments made during study implementation (i.e., during training, survey administration, or follow up contact with site administrators, youth workers and facilitators).
- f) Review and report any adverse events associated with the study.

8.3 ADVERSE EVENTS AND SERIOUS ADVERSE EVENTS

8.3.1 DEFINITION OF ADVERSE EVENTS

This study is of minimal risk to participants because there is low likelihood of any risk or adverse events to occur during administration of anonymous surveys and confidential interviews. Precautions will be implemented to protect participating subjects' privacy and confidentiality. The primary risks are risk for breach of confidentiality and potential for emotional distress related to answering survey questions, both highly unlikely events.

Should a participant disclose safety concerns during the course of programming, the site RA follows the emotional distress protocol and immediately notifies [name] (PI), a plan for safety and any reporting requirements are addressed, and the RA completes a report. Such events are reported to the IRB.

8.3.2 DEFINITION OF SERIOUS ADVERSE EVENTS

We follow the definition of serious adverse events as outlined by the University of Pittsburgh Human Subjects Research Protection Office, and any questions we have about specific events, we review with a representative from this office.

While we do not anticipate any serious adverse events, we will promptly report to the IRB any unintended or unanticipated consequences from participating in this study. If any serious adverse event occurs (death, life threatening, new, serious, or permanent disability), it will be reported within 72 hours to the IRB. Specific information that will be recorded on the adverse event form will include details of the adverse event, treatment required for the event, the participant's condition after the event, an estimate of the extent of injury, and ways to prevent similar events from occurring in the future. [name] will classify the relationship of the study protocol to the event on a scale from not related to highly probably

related as outlined by the IRB, and severity of the event from mild to severe based on a degree of intensity outlined by the IRB, which will be reviewed by the IRB.

All adverse events will be reported to the National Institutes of Health in addition to the University of Pittsburgh Human Research Protection Office.

